3.1.3. Double-Blind Treatment Phase

The day after the Baseline Visit, patients will take their first dose of study drug in the 3-week Titration Period (Day 1) (Figure 1). Patients will be titrated to their randomized stable dose of study drug in accordance with the schedule presented in Table 7; study drug dose will be titrated on Day 8 and again on Day 15 (as appropriate based on randomized stable dose, per Table 7), with all patients at their randomized stable dose by Day 15 of the Titration Period. At the end of the 3-week Titration Period, patients will continue to take study drug (pitolisant or placebo) in accordance with their randomized stable dose once daily in the morning upon wakening for an additional 8 weeks (Stable Dose Period; Days 22 to 77) for a total of 11 weeks of double-blind treatment.

Table 7: Study Drug Dosing in the Double-Blind Treatment Phase

| | | Titration Period ^a (3 Weeks) | | | | | | |
|-------------------------------------|------------------------|--|--------------------------|--------------------------------|--|--|--|--|
| Age/Treatment Groups | Week 1 (Days 1 - 7) | Week 2 (Days 8 - 14) | Week 3 (Days 15 - 21) | Weeks 4 - 11 (Days 22 - 77) | | | | |
| Pediatric patients (6 to <12 years) | | | | | | | | |
| Lower dose pitolisant | 4.45 mg | 8.9 mg | 8.9 mg | 8.9 mg | | | | |
| Higher dose pitolisant | 4.45 mg | 8.9 mg | 17.8 mg | 17.8 mg | | | | |
| Placebo | Matching tablets | Matching tablets | Matching tablets | Matching tablets | | | | |
| Adolescent patients (12 to <18 | 3 years) | | | | | | | |
| Lower dose pitolisant | 4.45 mg | 8.9 mg | 13.35 mg | 13.35 mg | | | | |
| Higher dose pitolisant | 8.9 mg | 17.8 mg | 26.70 mg | 26.70 mg | | | | |
| Placebo | Matching tablets | Matching tablets | Matching tablets | Matching tablets | | | | |
| Adult patients (18 to 65 years |) | | | | | | | |
| Lower dose pitolisant | 4.45 mg | 8.9 mg | 17.8 mg | 17.8 mg | | | | |
| Higher dose pitolisant | 8.9 mg | 17.8 mg | 35.6 mg | 35.6 mg | | | | |
| Placebo | Matching tablets | Matching tablets | Matching tablets | Matching tablets | | | | |

^a Study drug dose will be titrated on Day 8 and again on Day 15 (as appropriate based on randomized stable dose); all patients will be at their randomized stable dose by Day 15.

Adjustments to study drug dosing outside the protocol-specified titration schedule are not permitted during the 11-week Double-Blind Treatment Phase of the study.

Patients and/or their caregivers will receive telephone calls (TCs) from the study site on Days 8 and 15 (± 3 days) (TCs 1 and 2, respectively) during the 3-week Titration Period to assess for AEs and concomitant medication use, complete the C-SSRS, and review/confirm titration of study drug dose. During the 8-week Stable Dose Period, patients will complete safety, efficacy, and PK assessments at the study site on Day 22 (Visit 3), Day 50 (Visit 4), and Day 77 (Visit 5) (window for Visits 3, 4, and 5 is ± 3 days), and patients and/or their caregivers will receive TCs

^b Study drug doses for the Stable Dose Period; dose adjustments outside the protocol-specified titration schedule are not permitted in the Double-Blind Treatment Phase.

from the study site on Days 29, 36, and 57 (±3 days) to assess for AEs and concomitant medication use, complete the C-SSRS and ADAMS, and confirm study drug dose.

At the end of the Double-Blind Treatment Phase, eligible patients will be given the opportunity to enter an optional OLE Phase (Section 3.1.4). If a patient does not enter the OLE Phase, the patient and/or their caregiver will receive Safety Follow-up TCs from the study site 15 (±3 days) and 30 days (+3 days) after their final dose of blinded treatment to assess for AEs (including inquiries regarding signs and symptoms of arrhythmia, any other cardiac manifestations [e.g., syncope], and psychiatric events [e.g., suicidality, compulsive behavior, anxiety]) and use of concomitant medications and to complete the C-SSRS and ADAMS (Section 7.5).

3.1.4. Open-Label Extension Phase

Before patients can enter the OLE Phase of the study, eligibility criteria must be confirmed at Visit 5 in the Double-Blind Treatment Phase.

Patients who discontinue early from the Double-Blind Treatment Phase of the study but wish to enter the OLE Phase will require approval from the Medical Monitor in consultation with the Investigator (eligibility criteria must be confirmed).

In the OLE Phase, prior to implementation of Amendment 6, patients received a maximum target dose of pitolisant based on their age (17.8 mg for ages 6 to <12 years, 26.7 mg for ages 12 to <18 years, or 35.6 mg for ages 18 to 65 years) as detailed in Table 8.

Adjustments to pitolisant dose are permitted in the OLE Phase. Details for pitolisant dose adjustments are provided in Section 3.1.5.2.

Eligible patients will be dispensed open-label pitolisant at Visit 5 (Day 77 ± 3 days) of the Double-Blind Treatment Phase and will take their first dose of open-label pitolisant in the morning the following day (Day 78 ± 3 days). Patients will continue to take open-label pitolisant once daily in the morning upon wakening through the end of the study.

 Table 8:
 Pitolisant Dosing in the Open-Label Extension Phase

| | | Long-Term Dosing Period | | |
|---------------------------------------|-------------------------|----------------------------|-------------------------|----------------------------|
| Age Groups | Week 12 Days 78 - 84 | Week 13 Days 85 - 91 | Week 14 Days 92 - 98 | Week 15 (Day 99) to EOT |
| Pediatric patients (6 to <12 years) | 4.45 mg | 8.9 mg | 17.8 mg | 17.8 mg |
| Adolescent patients (12 to <18 years) | 8.9 mg | 17.8 mg | 26.7 mg | 26.7 mg |
| Adult patients (18 to 65 years) | 8.9 mg | 17.8 mg | 35.6 mg | 35.6 mg |

EOT = End of Treatment; OLE = Open-Label Extension

Patients and/or their caregivers will receive TCs from the study site on Days 85 and 92 (±3 days) to assess for AEs and concomitant medication use, complete the C-SSRS, and review/confirm pitolisant dose titration. Patients and their caregivers will complete safety and effectiveness assessments on Day 99 (±3 days; Visit 6) and approximately every 90 days (±7 days) thereafter up to Day 369 (i.e., Days 189 [Visit 7], 279 [Visit 8], and 369 [Visit 9]).

After completion of Visit 9, patients and/or their caregivers will be contacted by telephone on Day 459 (±7 days; TC 8), after which patients and their caregivers will return for an on-site study visit on Day 549 (±7 days; Visit 10). This pattern of alternating TCs and on-site study visits approximately every 3 months will be repeated until either the patient withdraws from the study, or the study is terminated by the Sponsor. During the first year of the OLE Phase of the study, patients will have the option to complete up to two of the scheduled on-site study visits remotely (i.e., two of Visits 6, 7, 8, and 9); thereafter (i.e., after Visit 9/Month 12), patients will have the option to complete one of the two scheduled on-site study visits remotely per year. At the TCs, AEs and concomitant medications will be recorded, the C-SSRS will be completed, and the current dose of pitolisant and receipt of study drug shipments will be confirmed (Section 7.4.2.2). Safety, effectiveness, and study drug compliance will be assessed at the on-site study visits as detailed in Section 7.4.2.3. All patients will complete an End of Treatment (EOT) Visit as outlined in Section 7.4.2.4.

Patients and/or their caregivers will receive Safety Follow-up TCs from the study site 15 days (±3 days) and 30 days (+3 days) after their final dose of open-label pitolisant to assess for AEs (including inquiries regarding signs and symptoms of arrhythmia, any other cardiac manifestations [e.g., syncope], and psychiatric events [e.g., suicidality, compulsive behavior, anxiety]) and use of concomitant medication and to complete the ADAMS (Section 7.5).

3.1.5. Dose Adjustments

3.1.5.1. Double-Blind Treatment Phase

Adjustments to the dose of study drug outside of the protocol-specified titration schedule are not permitted during the 11-week Double-Blind Treatment Phase.

3.1.5.2. Open-Label Extension Phase

Adjustments in pitolisant dose are permitted in the OLE Phase.

Prior to implementation of Amendment 6, pitolisant doses could be adjusted (higher or lower) in 4.45 mg increments based on Investigator assessment of clinical response, tolerability and/or patient age.

After implementation of Amendment 6, pitolisant dose may be adjusted (higher or lower) based on Investigator discretion in consultation with the Medical Monitor up to the maximum daily dose allowed (Table 9).

In the event a patient develops moderate hepatic impairment (Child-Pugh B) or moderate or severe renal impairment during the study, the dose of pitolisant may need to be decreased by the Investigator in consultation with the Medical Monitor. Patients who develop either end-stage renal disease (estimated glomerular filtration rate [eGFR] of <15 mL/minute/1.73 m²) or severe hepatic impairment (Child-Pugh C) must be withdrawn from the study (Section 4.4.1).

If a patient began taking a strong CYP2D6 inhibitor during the OLE Phase, prior to implementation of Amendment 6, pitolisant dose was to be reduced by one half of the maximum age-based dose (Table 8).

If a patient begins taking a

strong CYP3A4 inducer during the OLE Phase, pitolisant dose may be increased up to the maximum permitted daily dose based on the patient's age (prior to implementation of Amendment 6)

3.1.6. Dose Interruptions

Every effort should be made to educate patients/caregivers/parent(s)/legal guardian(s) on the importance of remaining compliant with study drug dosing.

No interruptions in study drug dosing are expected in the Double-Blind Treatment Phase of the study. If a dose is missed in the Double-Blind Treatment Phase, the patient should take the next dose the following morning upon wakening. If dosing is interrupted (e.g., due to an AE) for 7 or more days, consult with the Medical Monitor before restarting study drug.

In the OLE Phase of the study, interruptions in study drug dosing are permitted based on tolerability and the discretion of the Investigator. If a dose is missed in the OLE Phase, the patient should take the next dose the following morning upon wakening.

If a patient is taking a pitolisant dose that is >8.9 mg and has a dosing interruption exceeding 7 days in the OLE Phase, before restarting study drug, the Investigator should consult with the Medical Monitor.

3.2. Study Endpoints

3.2.1. Efficacy Endpoints

3.2.1.1. Double-Blind Treatment Phase

3.2.1.1.1. Primary Efficacy Endpoint

The primary efficacy endpoint is the change in mean ESS-CHAD (parent/caregiver version) score from Baseline to Week 11 for pitolisant compared with placebo.

3.2.1.1.2. Key Secondary Efficacy Endpoints

Change from Baseline to Week 11 for pitolisant compared with placebo in:

- CaGI-S for EDS
- CGI-S for overall clinical status related to PWS

3.2.1.1.3. Other Secondary Efficacy Endpoints

Change from Baseline to Week 11 for pitolisant compared with placebo in:

- Behavior as measured by the ABC-C
- Behavioral and cognitive rigidity as measured by the MERS-R-PWS
- Psychomotor function as measured by the Cogstate Detection Test
- Attention as measured by the Cogstate Identification Test
- Working memory as measured by the Cogstate One Back Test
- Measure of caregiver burden using the ZBI-22

3.2.1.1.4. Exploratory Endpoints

Change from Baseline to Week 11 for pitolisant compared with placebo in:

- Total score of the HQ-CT in conjunction with the FSZQ
- Acylated and unacylated ghrelin levels

3.2.1.2. Open-Label Extension Phase

Long-term effectiveness of pitolisant as measured by ESS-CHAD (parent/caregiver version), CaGI-S for EDS, CGI-S for overall clinical status related to PWS, ABC-C, MERS-R-PWS, Cogstate Detection Test, Cogstate Identification Test, Cogstate One Back Test, ZBI-22, and HQ-CT in conjunction with the FSZQ will be assessed during the patient's first year of participation in the OLE Phase of the study. After the first year of participation, effectiveness measures will include the ESS-CHAD (parent/caregiver version) as reported by caregivers, CaGI-S, and CGI-S.

3.2.2. Pharmacokinetic and Pharmacodynamic Endpoints

• C_{max} of pitolisant and its major metabolite, BP1.3484

- Area under the concentration-time curve from time 0 to the last collection time (AUC_{last}) after administration of pitolisant
- Time to observed maximum concentration (t_{max}) of pitolisant
- Exposure-response relationship between pitolisant levels and change in efficacy measures

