- The appetite-stimulating hormone ghrelin is produced by ghrelinergic cells in the gut and acts as a peripheral orexigenic signal that communicates with the arcuate nucleus of the hypothalamus to increase appetite and food intake in response to fasting (Khan et al 2018). In healthy individuals, fasting promotes increased secretion of ghrelin in the gut, and levels decrease after eating; however, this does not occur in patients with PWS. Children and adults with PWS have between 3.0- and 4.5-fold higher fasting plasma levels of ghrelin compared with matched control patients with obesity (Cummings et al 2002; DelParigi et al 2002; Haqq et al 2003), and ghrelin levels may influence eating behavior in these patients (Allas et al 2018). The mechanism underlying ghrelin dysregulation and the functional impact of elevated ghrelin levels on symptoms of PWS, including hyperphagia, are currently unknown; however, a link between ghrelin and the histaminergic system has been suggested by studies investigating the gastroprotective role of ghrelin in the gut (Adami et al 2010). In this study, serum ghrelin levels (acylated and unacylated) will be evaluated (Section 6.3.10).

Standard safety and tolerability assessments will include adverse event (AE) monitoring, clinical laboratory tests, vital signs, 12-lead electrocardiograms (ECGs), physical examinations, and suicidality. In addition, anxiety will be assessed using the Anxiety, Depression, and Mood Scale (ADAMS), and the frequency, type, and duration of seizures in patients with a history of seizure disorder will be collected (Section 6.5.6).

Characterization of the pharmacokinetics (PK) of pitolisant will inform the optimal dose selection strategy. Pitolisant is primarily metabolized by cytochrome P450 (CYP) 2D6 and to a lesser extent by CYP3A4; metabolites are further metabolized or conjugated with glycine or glucuronic acid. None of the pitolisant metabolites are pharmacologically active. BP1.3484 is the most predominant metabolite after repeat dosing with pitolisant, and PK analyses in this study will include evaluation of this major metabolite.

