7.3.2.3. Visit 4 (Day 50 ± 3 Days)

To accommodate PK sample collection at Visit 4, patients will not take their daily dose of study drug before arriving at the study site. Patients and their caregivers will bring study drug and study diary with them to the study visit (time of study drug administration on the day before Visit 4 should be recorded in the study diary).

Study drug administration will be at the study site; the timing of study drug administration will be based on the PK sampling schedule.

Blood Sample Collection for PK:

A blood sample for PK analyses will be collected before administration of study drug at the study site (the time of sample collection is to be recorded).

After the first blood sample for PK analyses is collected, patients will be administered study drug (the time of study drug administration is to be recorded).

Additional blood samples for PK analyses will be collected at the following times after study drug administration (the time of each blood sample collection is to be recorded):

- Between 45 and 75 minutes after dosing
- Between 1.5 and 2.5 hours after dosing
- Between 3.0 and 4.0 hours after dosing
- Between 5.0 and 6.0 hours after dosing

The following evaluations will also be performed at Visit 4:

- Urine pregnancy test (FCBP only)
- Abbreviated physical examination
- Body weight
- Vital signs
- 12-lead ECG (in triplicate)
- C-SSRS (Appendix M)
- ADAMS
- Clinical laboratory tests (serum chemistry, hematology, urinalysis)
- Review of AEs
- Review of concomitant medications
- ESS-CHAD (parent/caregiver version)
- CaGI-S (for EDS)
- CGI-S (for overall clinical status related to PWS)

- ABC-C
- MERS-R-PWS
- Cogstate Detection Test
- Cogstate Identification Test
- Cogstate One Back Test
- ZBI-22
- HO-CT
- FSZQ
- Review study drug compliance/accountability (Section 5.5 and Section 5.6)

Blood draw volumes at Visit 3 are not to exceed the maximal allowable of 3.0 mL/kg per day (Appendix A and Table 10).

Patients will be dispensed study drug at this visit.

7.3.2.4. Visit 5 (Day 77 ±3 Days); End of Treatment in the Double-Blind Treatment Phase

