12.5 PK Analyses

Plasma concentration-time data of pitolisant and BP1.3484 will be summarized using descriptive statistics by age group (6 to <12 years; 12 to <18 years, ≥18 years), treatment group, and scheduled sampling interval. The following summary statistics will be included for plasma concentration-time data: mean, SD, coefficient of variation (CV%), geometric mean, geometric SD, median, minimum, and maximum.

Plasma concentration-time profiles of pitolisant and BP1.3484 will be plotted on semi-log and linear scales for each individual patient as spaghetti plots by age group (6 to <12 years; 12 to <18 years, ≥18 years) and treatment group using actual collection times. For ease of presentation, mean plasma concentration-time data of pitolisant and BP1.3484 will be plotted separately by midpoint (on hour scale) for the planned interval on both linear and semi-logarithmic scales. Plasma PK concentrations of pitolisant and BP1.3484 for each individual will be reported to the precision of the raw data in listing presentations. In addition, concentration-time profiles for each analyte will be plotted by patient.

Values reported as below the lower limit of quantification (LLOQ) or below the limit of quantification (BLQ) i.e., reported as <LLOQ (BLQ) will be imputed to be 0.

If data allow, the following steady-state PK parameters will be calculated for each analyte as listed in Table 12.

Table 12: PK Parameters

Parameter	Description	PK Analysis Notes	Analyte	SAS Programming Notes
C _{max}	Maximum plasma concentration. Observed peak analyte concentration obtained directly from the experimental data without interpolation, expressed in concentration units.		Pitolisant and BP1.3484	Cmax from WinNonLin software (WNL) version 8.1.1 or later.
T _{max}	Time to reach C _{max} in plasma. The time to reach maximum concentration is obtained directly from the experimental data without interpolation and expressed in time units.		Pitolisant and BP1.3484	Tmax from WNL
AUC _(0-T)	Area under the concentration-time curve from time 0 (dosing) to the time of the last quantifiable concentration observed, without interpolation or extrapolation, using trapezoidal summation. AUC _(0-T) is expressed in concentration*time units.	Calculated by the linear up/log down method in WNL	Pitolisant and BP1.3484	AUClast from WNL

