AUC _(tau)	Area under the {plasma / serum} concentration-time curve over the sampling interval (time 0 to XXhr) using trapezoidal summation. The actual duration of tau is used to capture this parameter. To capture AUC _{tau} , the actual time deviation should be <10%.	Calculated by the linear up/log down method in WNL	Pitolisant and BP1.3484	AUC from WNL summary file at corresponding midpoint XX Flag to List only if: Percent difference in planned and actual sampling at tau ≥10%
C _{max} /D	Dose normalized maximum plasma concentration.		Pitolisant	Cmax / dose

Parameter	Description	PK Analysis Notes	Analyte	SAS Programming Notes
AUC _(0-T) /D	Dose normalized area under the concentration-time curve from time 0 (dosing) to the time of the last quantifiable concentration observed.	Calculated by the linear up/log down method in WNL	Pitolisant	AUClast / dose
C _{trough}	Observed plasma concentration immediately prior to dose.		Pitolisant and BP1.3484	Predose concentration (Day 22, 50, 77)

PK parameters will be summarized overall and by treatment group and age. The following summary statistics will be included for plasma concentration-time data: mean, SD, CV%, geometric mean, geometric SD, median, minimum, and maximum. Only the median, minimum, and maximum will be calculated for t_{max}.

The plasma concentration-time data from this study may be combined with data from previous studies that utilized the same bioanalytical method, and population PK analyses may be conducted as post hoc analysis; results will be provided in a separate report.

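### AUClast and its dose-normalised form end at each patient's own last quantifiable Visit 4 sample, so areas over about 3 to 6 h are averaged together by dose and age, with no rule for a missed last draw

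*Protocol*

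**What the plan says.** - **Endpoint.** Protocol 3.2.2 lists AUClast, the "Area under the concentration-time curve from time 0 to the last collection time", with no fixed end hour.
- **SAP definition.** SAP 12.5, Table 12, takes AUC(0-T), programmed as AUClast, "to the time of the last quantifiable concentration observed, without interpolation or extrapolation". The dose-normalised row, AUC(0-T)/D, has the same end: "Dose normalized area under the concentration-time curve from time 0 (dosing) to the time of the last quantifiable concentration observed". Under protocol 9.1 the SAP governs where the two documents differ.
- **Sampling.** Protocol 7.3.2.3 schedules a pre-dose sample and four post-dose samples at Visit 4. The last two are due "Between 3.0 and 4.0 hours after dosing" and "Between 5.0 and 6.0 hours after dosing". Dosing is once daily, and actual sampling times are recorded.
- **Summaries.** SAP 12.5 summarises PK parameters overall, by treatment group and by age. No sentence excludes, flags or lists separately an AUClast that stops at the 3 to 4 h sample.
- **A second AUC.** Table 12 also has an AUC(tau) row, for the "concentration-time curve over the sampling interval (time 0 to XXhr) using trapezoidal summation". It uses the actual duration, requires a time deviation below 10%, and makes values at 10% or more list-only. The end hour reads XX, and alternatives for plasma and serum still stand in braces, so the row looks like an unfilled template entry.
- **Purpose.** Protocol 1.2 states: "Characterization of the pharmacokinetics (PK) of pitolisant will inform the optimal dose selection strategy".

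**The concern.** An area under a curve depends on how long it runs. The sampled part of the profile covers at most 6 h of a 24 h dosing interval, so if concentrations are still appreciable at the cut, AUClast grows with the clock time of the last sample. Two patients with identical pharmacokinetics can then get different values because one was bled at 5.0 h and the other at 6.0 h, or because one missed the last draw.

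These values go into means and geometric means in small age-by-dose cells. At the least this inflates the variability reported for exposure. At worst, if one age or dose group misses the last draw more often, its exposure would look too low. Dividing by dose does not help, because the dose-normalised AUC has the same variable end.

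**Working it through.** The documents give no AUC duration or PK precision figure, so there is no stated number to reproduce.

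**1. Length of the area (protocol 7.3.2.3 windows).**
- Last draw on time: 5.0 to 6.0 h; 6.0/5.0 = 1.20.
- Last draw missed, midpoint against midpoint: 3.5/5.5 = 0.64.
- Extremes: 3.0/6.0 = 0.50.

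**2. What the AUC(tau) rule would catch.** XX is blank. Assume the planned time is the window midpoint, 5.5 h.
- Draw at 5.0 or 6.0 h: 0.5/5.5 = 9.1%. This passes the 10% rule, so the 5-versus-6 h spread stays in the summary because actual duration is used.
- Profile ending at 4.0 h: 1.5/5.5 = 27.3% short. At 3.0 h: 2.5/5.5 = 45.5% short. Both become list-only.
- The rule stands in the AUC(tau) row only. It does not govern AUC(0-T) or AUC(0-T)/D.

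**3. Effect on the area.** The rate constants are not in the documents, so a model has to be assumed: one compartment, oral, steady state, 24 h dosing,

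C(t) ∝ ka/(ka − ke) × [e^(−ke·t)/(1 − e^(−24ke)) − e^(−ka·t)/(1 − e^(−24ka))], with ke = ln 2 / half-life.

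Samples are at 0, 1, 2 and 3.5 h (window midpoints) plus the last draw. Each segment of length d uses the SAP's linear-up/log-down rule: d(C1 + C2)/2 when rising, d(C1 − C2)/ln(C1/C2) when falling.

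| Comparison, same patient | ka 0.4–1.5 per h, half-life 7–20 h | ka 0.4–3 per h, half-life 5–30 h |
|---|---|---|
| AUC(0–6)/AUC(0–5) | 1.18 to 1.24 | 1.15 to 1.24 |
| AUC(0–3.5)/AUC(0–5.5) | 0.56 to 0.64 | 0.56 to 0.68 |

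On the wider range, a draw at 6 h instead of 5 h adds 15 to 24%, and stopping at 3.5 h instead of 5.5 h removes 32 to 44%. A separate run with exact integration, half-life 5 to 30 h and tmax 1 to 3.5 h gave AUC(0–5)/AUC(0–6) of 0.82 to 0.88 (6 h adds about 14 to 22%) and AUC(0–3.5)/AUC(0–5.5) of 0.58 to 0.70.

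**4. Effect on a cell mean.** Protocol 9.2 plans 20 patients per dose group. Assume three equal age bands: 20/3 ≈ 6.7 per cell. Randomisation is not stratified by age (protocol 3.1.2), so actual cells may be smaller or larger. One profile ending at 3.5 h moves the mean of otherwise similar patients by 32%/7 ≈ 5% to 44%/6 ≈ 7%.

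**5. Does a common interval cure it?** Cut at 5.0 h. When concentration is falling, interpolate from a 6.0 h draw as C(5) = C(3.5) × [C(6)/C(3.5)]^(1.5/2.5); when rising, linearly. Over the wider range in step 3, the resulting AUC(0–5) is within 0.5% of the value with a draw at exactly 5.0 h. The timing effect of 15 to 24% all but disappears.

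**The case against.** The best reply is that the SAP already plans an AUC with a timing check. If XX is about 5.5 h, the AUC(tau) list-only rule keeps every profile ending at 3 to 4 h out of that summary, and so deals with the largest distortion for that one parameter. This stands: it would be wrong to say that the plan has no safeguard. But the hour is blank, all on-time draws pass on actual duration, and neither the listed endpoint nor the dose-normalised AUC is covered.

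Three more points stand. PK is an exploratory objective and is summarised without testing. Nothing ties draw time within the window to age or dose, so that part is noise. Cmax and the trough concentration do not depend on the length of the area.

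A reader might go further and infer any of the following, which the documents do not support:

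- **That the age-based doses rest on this comparison.** Protocol 1.3.1 bases them on earlier data, including single-dose PK data from 24 paediatric patients with narcolepsy. Protocol 1.3.2 bases the later extension regimens on efficacy signals, population PK simulations and safety data. The exposure-response plots in SAP 12.4.1.6.6 use concentrations, not AUClast.
- **That the PK population definition lets short profiles in.** SAP 6.1 widened it so that concentrations are reported even where parameters cannot be determined, and SAP 12.5 calculates parameters only if the data allow. The gap is the missing rule for AUClast.
- **That paediatric exposure will be biased low.** That needs missed last draws to be more frequent in the youngest patients, and no rate is given.

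**Conclusion.** The point holds for AUC(0-T) and AUC(0-T)/D. As written, areas over about 3 to 6 h are averaged by treatment and age, with no rule for profiles that lack the 5 to 6 h sample. For one patient the effect is about 15 to 24% across the last window and about 32 to 44% for a missed last draw. These figures rest on an assumed one-compartment model with absorption rate 0.4 to 3 per h and half-life 5 to 30 h; only the lengths of time come from the documents.

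The consequence is mainly extra noise in descriptive exposure summaries. Bias between age or dose groups is possible but conditional on unequal missed draws. No efficacy or safety conclusion is affected. The change is worth making because AUClast is the listed endpoint, the cells are small and the remedy uses data already collected.

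**What to change.** In SAP 12.5, Table 12, with matching wording in protocol 3.2.2 and 9.4.4:

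1. Complete or replace the AUC(tau) row with a partial AUC over a fixed interval that every in-window profile reaches, for example 0 to 5 h, interpolated at 5.0 h from actual times by the linear-up/log-down rule already stated. Give it a name that cannot be confused with the dosing-interval AUCtau of protocol 1.3.2.
2. Base the dose-normalised AUC on this parameter.
3. Summarise AUClast only for patients with the 5 to 6 h sample, and list the others.
4. Report by age and dose group how many patients lack that sample.

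The cost is one partial-area setting in the planned PK software and a few lines of text; no new samples or visits are needed. There are two drawbacks. Patients without the last draw leave the AUC summaries, though not Cmax or the listings; if they differ from the rest, truncation is exchanged for selection, which is why item 4 is needed. And up to 1 h of observed profile is left out of the common-interval AUC.
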